9 SAFETY MANAGEMENT

We plan to apply for NC TraCS DSMB support if the IRB approves of the study. We will submit ongoing reports to the committee according to the frequency of reports that is stipulated if the study is accepted by the DSMB. We anticipate that they will request an interim review after 10 subjects have completed the study.

Serious adverse event (SAE) or serious suspected adverse reaction. An adverse event (AE) or suspected adverse reaction is considered "serious" if, in the view of either the investigator, it results in any of the following outcomes: death, a life-threatening adverse event, inpatient hospitalization or prolongation of existing hospitalization, a persistent or significant incapacity or substantial disruption of the ability to conduct normal life functions, or a congenital anomaly/birth defect. Important medical events that may not result in death, be life-threatening, or require hospitalization may be considered serious when, based upon appropriate medical judgment, they may jeopardize the patient or subject and may require medical or surgical intervention to prevent one of the outcomes listed in this definition. Examples of such medical events include allergic bronchospasm requiring intensive treatment in an emergency room or at home, blood dyscrasias or convulsions that do not result in inpatient hospitalization, or the development of drug dependency or drug abuse.

Unanticipated problems involving risks to participants or others to include, in general, any incident, experience, or outcome that meets all of the following criteria:

- Unexpected in terms of nature, severity, or frequency given (a) the research procedures that are described in the protocol-related documents, such as the IRB-approved research protocol and informed consent document; and (b) the characteristics of the participant population being studied;
- Related or possibly related to participation in the research ("possibly related" means there is a reasonable possibility that the incident, experience, or outcome may have been caused by the procedures involved in the research); and
- Suggests that the research places participants or others at a greater risk of harm (including physical, psychological, economic, or social harm) than was previously known or recognized.

For AEs not included in the protocol defined grading system, the following guidelines will be used to describe severity.

- **Mild** – Events require minimal or no treatment and do not interfere with the participant's daily activities.
- **Moderate** – Events result in a low level of inconvenience or concern with the therapeutic measures. Moderate events may cause some interference with functioning.
- **Severe** – Events interrupt a participant's usual daily activity and may require systemic drug therapy or other treatment. Severe events are usually potentially life-threatening or incapacitating.

For all collected AEs, the clinician who examines and evaluates the participant will determine the AE's causality based on temporal relationship and his/her clinical judgment. The degree of certainty about causality will be graded using the categories below.

- **Definitely Related** – There is clear evidence to suggest a causal relationship, and other possible contributing factors can be ruled out. The clinical event, including an abnormal laboratory test result, occurs in a plausible time relationship to diet administration and cannot be explained by concurrent disease or other drugs or chemicals. The event must be pharmacologically or phenomenologically definitive, with use of a satisfactory rechallenge procedure if necessary.
- **Probably Related** – There is evidence to suggest a causal relationship, and the influence of other factors is unlikely. The clinical event, including an abnormal laboratory test result, occurs within a reasonable time after administration of the diet, is unlikely to be attributed to concurrent disease or other drugs or chemicals, and follows a clinically reasonable response on withdrawal (dechallenge). Rechallenge information is not required to fulfill this definition.
- **Possibly Related** – There is some evidence to suggest a causal relationship (e.g., the event occurred within a reasonable time after administration of the trial diet). However, other factors may have contributed to the event (e.g., the participant's clinical condition, other concomitant events). Although an AE may rate only as "possibly related" soon after discovery, it can be flagged as requiring more information and later be upgraded to "probably related" or "definitely related," as appropriate.
- **Unlikely to be related** – A clinical event, including an abnormal laboratory test result, whose temporal relationship to diet administration makes a causal relationship improbable (e.g., the event did not occur within a reasonable time after administration of the trial medication) and in which other drugs or chemicals or underlying disease provides plausible explanations (e.g., the participant's clinical condition, other concomitant treatments).
- **Not Related** – The AE is completely independent of study diet administration, and/or evidence exists that the event is definitely related to another etiology. There must be an alternative, definitive etiology documented by the clinician].

The study physician, [name], will be responsible for determining whether an AE is expected or unexpected. An AE will be considered unexpected if the nature, severity, or frequency of the event is not consistent with the risk information previously described for the study agent.

The occurrence of an AE or SAE may come to the attention of study personnel during study visits and interviews of a study participant presenting for medical care, or upon review by a study monitor.

All AEs including local and systemic reactions not meeting the criteria for SAEs will be captured on the appropriate CRF. Information to be collected includes event description, time of onset, clinician's assessment of severity, relationship to study product (assessed only by those with the training and authority to make a diagnosis), and time of resolution/stabilization of the event. All AEs occurring while on study must be documented appropriately regardless of relationship. All AEs will be followed to adequate resolution.

Any medical condition that is present at the time that the participant is screened will be considered as baseline and not reported as an AE. However, if the study participant's condition deteriorates at any

time during the study, it will be recorded as an AE. UPs will be recorded in the data collection system throughout the study.

Changes in the severity of an AE will be documented to allow an assessment of the duration of the event at each level of severity to be performed. AEs characterized as intermittent require documentation of onset and duration of each episode.

The PI will record all reportable events with start dates occurring any time after informed consent is obtained until 7 (for non-serious AEs) or 30 days (for SAEs) after the last day of study participation. At each study visit, the investigator will inquire about the occurrence of AE/SAEs since the last visit. Events will be followed for outcome information until resolution or stabilization.

AEs will be reported to the IRB within 24h after the study physician becomes aware of them.

The study physician shall report Serious Adverse Events to the IRB as soon as possible, but in no event later than 24 h after the investigator first learns of the event.

To satisfy the requirement for prompt reporting, Unexpected problems (Ups) will be reported using the following timeline:

- UPs that are SAEs will be reported to the IRB within 24h of the investigator becoming aware of the event.
- Any other UP will be reported to the IRB within 10 days of the investigator becoming aware of the problem.

Data Safety Monitoring Plan: Participant confidentiality is strictly held in trust by the participating investigators and their staff. This confidentiality is extended to cover testing of biological samples and genetic tests in addition to the clinical information relating to participants. Therefore, the study protocol, documentation, data, and all other information generated will be held in strict confidence. No information concerning the study or the data will be released to any unauthorized third party.

The study participant's contact information will be securely stored for internal use during the study. At the end of the study, all records will continue to be kept in a secure location for as long a period as dictated by local IRB and Institutional regulations.

This study is a genome-wide association study and will comply with the NIH Policy for Sharing of Data Obtained in NIH Supported or Conducted GWAS, which calls for investigators funded by the NIH for GWAS to 1) share de-identified genetic (genotypic and phenotypic) data through a centralized NIH data repository; and 2) submit documentation that describes how the institutions have considered the interests of the research participants, such as privacy and confidentiality. Submission of data to the NIH GWAS repository will be consistent with the permissions and limitations delineated on the study consent signed by study participants.

Intended use of stored samples, specimen or data. We will store DNA from each subject so that we can measure gene polymorphisms and other variants that are discovered by others to be relevant to choline metabolism after the completion of this study.

We will store plasma from each subject so that we can measure metabolites and other biomarkers are discovered by others to be relevant to choline metabolism after the completion of this study.

With the participant's approval de-identified biological samples will be stored at -80 degrees C in freezers at the UNC Nutrition Research Institute.

Study participants who request destruction of samples will be notified of compliance with such request and all supporting details will be maintained for tracking.

Access to stored samples will be limited to study investigators. Samples and data will be stored using codes assigned by the investigators. Data will be kept in password-protected computers. Only investigators will have access to the samples and data.

10 DATA COLLECTION AND MANAGEMENT

[name] (PI) and the medical director [name] will monitor subject data for safety continuously throughout the study and as new subjects are recruited. Data will be transmitted electronically via secured email communications among study personnel, including [name], [name], [name], [name], and [name]. All data transmission between team members will use the study ID to reference individual participation. De-identified data will be transmitted in SAS via encrypted hard drives or via secure UNC email accessed through a secure network. Sharing of data by email will use the secure protocol required of University personnel.

Once the study has ended, data and human biological specimens will be labeled only with coded study IDs for duration of the study and analysis and should not be identifiable in any way. Personally identifiable data collected for the purpose of payment to study subjects for participation (SSN, name, address, etc.) will be located in locked offices. Any electronically stored information will be kept in password-protected files. Specimens will be stored indefinitely and not anonymized. The specimens will not be shared with other researchers.

Genetic samples will be banked and genotyping will be conducted at a later date when we are certain that a follow-on study will occur. Genetic samples mean DNA for genotyping. Identifiable data and biological materials from study subjects who do not sign the optional storage consent will be destroyed by deleting electronic files and shredding hard copy.

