6.2 Secondary Endpoint

SubAim 1c: Determine whether people with genetic polymorphisms known to increase risk for developing choline deficiency-induced organ dysfunction are also more likely to have a worse choline status score and a reduction in choline pool size assessed using isotope dilution. A number of SNPs in genes of choline and folate metabolism have been associated with increased risk for developing organ dysfunction on a low choline diet. We hypothesize that people with these SNPs have a lower choline pool size/worse choline status score for any given choline dietary intake than do people without these SNPs.

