score will be calculated based on the OPLS weights and the variability explained in OPLS-R. Biomarkers with $VIP > 1.5$ will be considered the most important biomarkers responsible for prediction. Pathway analysis will be performed using GeneGo metacore (Thomson Reuters, <https://portal.genego.com>) and QIAGEN's Ingenuity Pathway Analysis (IPA®, QIAGEN Redwood City, www.qiagen.com/ingenuity).

Statistical methods (SubAim 1c). Linear model with repeated measures will be used to identify SNPs that increase (or decrease) the risk for developing choline deficiency-induced organ dysfunction. This analysis will be performed for each diet period (healthy men, pre- and postmenopausal women) separately. In each linear model, the choline status score defined by Aim 1 is the response variable. Diet effect (fixed), genotype effect (fixed), subject effect (random) and diet \times genotype interaction effect are the independent variables. In the repeated measures design, each subject serves as his/her own control. Therefore, confounding effect from genotype is not our concern. However, it is possible that genotype serves as a moderator, which interacts with the diet effect, and affects the direction or strength of the diet effect. For example, the change in choline status score in responding to dietary choline may be observed in subjects with one genotype (responders), but not in subjects with other genotypes (non-responders). The genotypes that modify the diet effect will be identified by the diet \times genotype interaction term. This analysis will be performed in the MIXED procedure in SAS (SAS Institute, Inc., Cary, NC). Benjamini-Hochberg method for False Discovery Rate (FDR) correction will be used for multiple testing correction. To improve the normality of the data, data transformation such as log transformation will be applied to metabolomics data, and outliers with studentized residue > 3 or < -3 will be excluded. Post hoc comparisons will be performed to identify metabolites associated with different levels of dietary choline and different genotypes. The analysis described above will also be applied to choline pool size data to identify significant diet \times genotype interaction effect for choline pool size.

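### Section 10 makes genotyping wait on a certain follow-on study, which contradicts the genotype-based secondary endpoint (SubAim 1c) planned for this study

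*Combined protocol and SAP*

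**What the plan says.** Section 10 (Data Collection and Management) states that genetic samples are banked and that "genotyping will be conducted at a later date when we are certain that a follow-on study will occur". The next sentence defines the term: "Genetic samples mean DNA for genotyping". The same paragraph says that identifiable data and "biological materials from study subjects who do not sign the optional storage consent will be destroyed". The means it gives are deletion of files and shredding of paper, and it gives no time.

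Section 6.2 (Secondary Endpoint) contains a single item, which begins "SubAim 1c: Determine whether people with genetic polymorphisms known to increase risk". Its hypothesis is explicit: "We hypothesize that people with these SNPs have a lower choline pool size/worse choline status score for any given choline dietary intake". That comparison needs a genotype for each person analysed.

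Other sections treat genotyping as part of this study:
- Section 4.2, Visit 1: saliva is collected for DNA.
- Section 5.1, Genotyping: RT-PCR for one PEMT SNP and a custom array for the rest.
- Section 6.3: a repeated-measures model with genotype and diet-by-genotype terms.
- Section 6.4: 89.61% power for an interaction effect of 0.6, followed by the same analysis for the more than 2 million other SNPs, which are described as measured in this study.
- Section 9: the study is called a genome-wide association study and is committed to the NIH data-sharing policy.

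**The concern.** A secondary endpoint with its own model and power statement should not depend on an event outside the trial. Section 10 makes it do so, because whether the DNA is ever genotyped turns on a later decision about another study.

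More is at stake than one analysis. Section 5.1 presents SubAim 1c as a test of the validity of the choline score and the isotope dilution measure, and Section 6.4 says the PEMT analysis confirms that the score agrees with existing knowledge. Section 6.3 declines a training and testing split and relies on the bootstrap for prediction error. The genotype comparison is therefore one of the few checks on the score that does not come from the fitting of the score itself.

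The storage consent adds a second exposure. If genotyping is deferred, DNA has to be kept until it happens, and Section 10 makes keeping material depend on an optional signature. Depending on the order of events, that signature could decide who enters the SubAim 1c analysis.

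**Working it through.** This is mainly a textual check, so the statements are set against each other and followed to their consequences.

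**1. Does the condition cover the SubAim 1c DNA or only surplus DNA?** The Section 9 text on stored samples speaks of DNA kept for variants found relevant after the study ends. Section 10 could have been meant in that sense. But it defines genetic samples as the DNA for genotyping, with no exemption for the PEMT SNPs or for the array in Section 5.1. On its wording, the condition covers the SubAim 1c DNA.

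**2. Is it reconciled elsewhere?** Sections 4.2, 5.1, 6.2, 6.3, 6.4 and 9 mention no follow-on study. None gives Section 10 precedence, and none overrides it.

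**3. What happens under each reading?** The planned number of completers is 3 groups × 50 = 150 (Sections 3.3 and 6.4).

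| Reading followed | Follow-on confirmed? | Destruction covers DNA and precedes genotyping? | Genotyped completers |
|---|---|---|---|
| Sections 5.1 and 6 | not relevant | not relevant | up to 150 |
| Section 10 | no | not relevant | 0 |
| Section 10 | yes | no | up to 150, at a later date |
| Section 10 | yes | yes | 150 × s |

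Here s is the share who sign the optional storage consent. The documents give no value for s, and it could lie anywhere from 0 to 1. For scale only: each 10 percentage points of refusal would remove 150 × 0.10 = 15 completers, or 50 × 0.10 = 5 per group if refusal were even across groups. Those remaining would be self-selected.

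**4. Can the loss be put in terms of the stated power?** The plan's figure is 89.61% for an effect of 0.6 at P < 0.05. Section 6.4 does not give the number analysed, the genotype split, the scale of the effect or whether the test is two-sided. Under an assumed two-sided two-sample t test with d = 0.6, the noncentrality is d × √(n₁n₂/(n₁+n₂)). Two quite different bases come close to the stated figure:
- 120 women split 56/44: 0.6 × √(67.2 × 52.8/120) = 3.26, power 89.9%.
- 150 people split 74/26: 0.6 × √(111 × 39/150) = 3.22, power 89.3%.

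Neither is the repeated-measures interaction model of Section 6.3, which is to be fitted separately in men, premenopausal women and postmenopausal women. The basis of 89.61% cannot be recovered, so a reduced power after loss of DNA cannot be derived from it. The conclusion does not need one: with no genotypes there is no analysis, whatever the power formula.

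**The case against.** The strongest reply is that Section 10 is one sentence in a data-management section, set against a consistent and unconditional plan in Sections 4.2, 5.1, 6 and 9. A reader might infer from Section 10 that the secondary endpoint cannot be delivered. The documents do not support that: genotyping is planned and described, and delivery is conditional rather than impossible. This part of the objection stands, and the defect is best called an unreconciled contradiction.

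A reader might also infer that DNA from anyone who declines optional storage is destroyed before it is genotyped. That goes beyond the text. The destruction sentence does not name DNA, gives no time, and describes methods suited to records. The consent form is not in the text reviewed here, so the optional consent may already cover only retention after the study. Section 9 is itself unsettled: it says DNA will be stored from each subject, yet makes storage of samples depend on the participant's approval. Loss before genotyping is a possibility to be closed off, not a stated rule.

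Finally, the consequence is bounded. The synopsis (Efficacy Evaluations) says the study need not be powered for genotype differences, and Section 6.4 calls the array-wide analysis exploratory and under-powered. That limits the damage to the PEMT confirmation and the wider exploration. It does not excuse leaving the input data of the only named secondary endpoint dependent on an outside event.

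**Conclusion.** The contradiction is real and should be resolved. Confidence is high on that and lower on the storage consent. Applied as worded, with no follow-on study confirmed, Section 10 leaves SubAim 1c with 0 genotyped people out of 150 planned completers, and the genotype check on the score is lost with it. Aim 1, the primary objective, is untouched.

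The possible restriction to those who agreed to storage rests on two unstated points: that the destruction sentence includes DNA, and that destruction comes before genotyping. Its size is unknown because the documents give no storage consent rate. It is tempting to quote a specific fall in power, but that would need an assumed refusal rate and a pooled two-sample test that the plan does not use, so no such figure is offered.

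**What to change.** In Section 10, remove the follow-on condition for the SubAim 1c genotyping. State that DNA from every participant under the main consent is genotyped, by RT-PCR and array as in Section 5.1, before the SubAim 1c analysis. State that the optional storage consent governs only retention and later use, and that any destruction of DNA follows genotyping. Bring the Section 9 text on stored samples into line.

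If the sponsor does intend to defer genotyping, change the other side instead: relabel SubAim 1c in Sections 2.2 and 6.2 as conditional on a follow-on study, and withdraw the 89.61% power statement in Section 6.4.

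The cost of the first option is protocol wording and, if the consent form needs to change, IRB approval and the decision on re-consent that Section 12 already requires. The assays are already part of the plan, though they would have to be run within this study. This should be settled before any sample is destroyed, since that step cannot be undone.

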11 RECRUITMENT STRATEGY

All study subjects will volunteer for participation in the study by responding by telephone or in person to recruitment materials. Subjects who respond to recruitment materials will be asked questions from the screening questionnaire to insure they are eligible for participation in the study. Study subjects will be recruited from the Charlotte metro region. Flyers will be posted on college campuses and other public buildings. Recruitment ads will be placed on the website and listservs of the UNC Nutrition Research Institute and the North Carolina Research Campus. Interviews will be scheduled in private rooms. Telephone numbers and email addresses will be stored in locked cabinets.

